### Study Protocol

#### Aim

The aim of this randomized controlled trial was to determine the effect of three different ETT cuff pressure controls used in ICU patients receiving mechanical ventilator support using an ETT on preventing microaspiration of gastric content and on VAP development within 48 hours after intubation.

#### Study design

This is a single-blind randomized controlled trial that compares finger palpation of the pilot balloon, intermittent and continuous ETT cuff pressure used to prevent microaspiration of gastric content for ICU patients.

#### Study population

The population of the study consists of the patients hospitalized in the Internal Medicine, Neurology, Neurosurgery, General Surgery, Anesthesia, Isolation and Diseases ICU of University Hospital. Inclusion criteria for the sampling of the study are as follows: being 18 years and above, voluntariness of the patients or their relatives, and having a need of mechanical ventilator support with an ETT for 48 hours. The criteria of exclusion from the sample are as follows: having contraindication of semi-sitting position, having a contraindication to enteral nutrition, patients who have spent more than 48 hours on a mechanical ventilator at the initial assessment, having tracheostomy, gastroesophageal reflux disease (GERD), aspiration pneumonia or any suspicion of it, and nasal ETT intubation. Power analysis was done to determine the number of patients to be distributed to Group 1, Group 2, and the control groups. The power analysis was done using GPower 1.3.9.2 software. Thus, the significance level was  $\alpha=0.05$  (%5), the effect size was  $d=0.5$ , and the number of patients in each group was 51 for the power at  $1-\beta=0.80$ . Missing, bad or lost data (in case patients were exitus) were considered and the number of patients was designed to be 56 for each group

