### **Statistical analysis**

The data will be analyzed using Statistical Package for the Social Sciences (SPSS) for Windows 21.0 (IBM SPSS Statistics for Windows, Version 21.0. Armonk, NY: IBM Corp.) Software. They will be divided into groups by ensuring homogeneity according to gender. Patients' socio-demographic and clinical attributes, frequencies, percentage distribution, mean, and standard deviation will be provided.

Kolmogorov-Smirnov Test will be used to check the appropriateness of data to normal distribution. Independent two-sample t-test, one-way analysis of variance will be used for the relationships between the variables that fit the normal distribution, and the Mann Whitney U test will be used for the variables that do not fit the normal distribution. Pearson Chi-square significance test and Fisher Exact will be applied in the analysis of categorical data. All p values lower than 0.05 will be taken as significant in all results ( $p < 0.05$ ).

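### VAP is half of the stated aim, but the only power figure cannot apply to it, and no effect estimate or interval is planned for it

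*Combined protocol and SAP*

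**What the plan says.** The Aim section says that the three methods of cuff pressure control will be compared for their effect "on preventing microaspiration of gastric content and on VAP development within 48 hours after intubation". Both outcomes stand in one sentence and neither is ranked above the other.

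The Study population section contains the only sample-size reasoning. It sets alpha at 0.05 and states that "the effect size was $d=0.5$ , and the number of patients in each group was 51 for the power at $1-\beta=0.80". The number is then raised to 56 per group to allow for missing data and deaths. This statement names no outcome, no test and no sidedness.

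The Statistical analysis section assigns t-tests and one-way analysis of variance to normally distributed variables, Mann-Whitney to other variables, and Pearson chi-square or Fisher's exact test to categorical data. Its one rule of interpretation is "All p values lower than 0.05 will be taken as significant in all results". It plans no risk difference, other effect estimate or confidence interval. No section gives an expected VAP rate or a VAP difference that the trial is meant to detect.

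**The concern.** The effect size d is a standardised difference in means. It suits a continuous measure such as pepsin, but it says nothing about a comparison of two proportions. One of the two named aims therefore has neither a stated power nor a stated precision.

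What is at stake is how the VAP result can be read. With 51 to 56 patients per group, a worthwhile reduction in VAP can easily fail to reach p < 0.05. If only the p value is given, a reader cannot tell a result that excludes a useful effect from one that is too imprecise to say. An interval would show the difference, and the plan does not provide one.

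**Working it through.** **Inputs from the documents.** Alpha 0.05, power 0.80, d = 0.5, 51 per group, raised to 56 (Study population). Three equal groups (Study population). Chi-square or Fisher for categorical data (Statistical analysis).

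**Assumptions, because the documents are silent.** VAP is analysed as yes/no. Control VAP rates run from 10% to 60%. The effect of interest is a halving. Comparisons are pairwise, two-sided at 0.05, with no adjustment for multiplicity.

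**Step 1: reproduce the plan's own figure.** For a two-sample t-test with d = 0.5, alpha 0.05 and power 0.80:

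| Sidedness | n per group required | Power at 51 | Power at 56 |
|---|---|---|---|
| One-sided | 50.15, rounded up to 51 | 0.806 | 0.838 |
| Two-sided | 63.8, rounded up to 64 | 0.71 | 0.75 |

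The stated 51 matches a one-sided comparison of two means. This supports reading the figure as a mean-difference calculation. It also shows that 0.80 at 51 per group does not hold for a two-sided test.

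**Step 2: power for a halving of VAP.** The normal approximation is

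power ≈ Φ{ [ |p1 − p2|·√n − 1.96·√(2·p̄·(1 − p̄)) ] / √( p1(1 − p1) + p2(1 − p2) ) }.

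For 20% against 10% with n = 56, p̄ = 0.15:

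- 0.10 × √56 = 0.748
- 1.96 × √(2 × 0.15 × 0.85) = 0.990
- √(0.16 + 0.09) = 0.5
- (0.748 − 0.990)/0.5 = −0.48, so power ≈ 0.315

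Exact power sums the binomial probabilities of every pair of event counts for which the test gives p < 0.05. For this case it is 0.317 by Pearson chi-square, which agrees. The exact two-sided results are:

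| Control → halved rate | Pearson, n = 51 | Pearson, n = 56 | Fisher, n = 56 |
|---|---|---|---|
| 10% → 5% | 0.15 | 0.16 | 0.08 |
| 20% → 10% | 0.29 | 0.32 | 0.23 |
| 30% → 15% | 0.45 | 0.49 | 0.39 |
| 40% → 20% | 0.61 | 0.65 | 0.57 |
| 50% → 25% | 0.76 | 0.79 | 0.73 |
| 60% → 30% | 0.89 | 0.90 | 0.86 |

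Pearson power passes 0.50 at a control rate of about 31% with 56 per group and about 33% with 51 per group.

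**Step 3: detectable difference.** For 80% power at 56 per group (exact Pearson), VAP would have to fall from 20% to 3.8%, or from 30% to 9.6%.

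**Step 4: precision.** With 20% in both arms and 56 per group, the 95% half-width for the risk difference is 1.96 × √(2 × 0.2 × 0.8 / 56) = 0.148, or about 15 percentage points. An observed difference of zero would then be compatible with a 10-point fall, which is a halving from 20%.

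**The case against.** The strongest reply is that powering a trial on one main outcome is ordinary practice. The Study design section speaks only of microaspiration, and the Intervention and Assessment section describes only pepsin sampling. On that view VAP is secondary in all but name, and its low power is no fault. Much of this stands: the plan claims no power for VAP, and low power alone would not be a defect. What remains is that VAP's secondary status is never stated and that no estimate or interval is planned for it.

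A reader might infer more than the documents support, in three ways.

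- *That a non-significant VAP result will be reported as no effect.* The Statistical analysis section says only which p values count as significant. It does not say how the others will be worded.
- *That a halving of VAP would usually be missed.* This depends on a control rate that the documents do not give. Two-sided, it holds only below about one third; at 50% the power is 0.76 to 0.79. On the one-sided basis that reproduces the plan's 51, power for 30% to 15% is already about 0.57 to 0.60 by the normal approximation.
- *That the 0.80 is the power for pepsin.* The plan names no outcome, and two-sided the figure at 51 per group is 0.71. Restating it as the pepsin power would endorse a number that may not hold.

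The plan also does not define VAP or say how and when it is assessed. Treating it as a yes/no outcome tested by chi-square or Fisher is a reasonable inference, but it is an inference.

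**Conclusion.** The point holds in a limited form. The sole power statement is on a mean-difference scale and cannot cover VAP, and the planned VAP analysis yields a p value with no measure of effect or uncertainty. For a halving at 51 to 56 per group, two-sided Pearson power runs from about 0.15 at a 10% control rate to 0.79 at 50%. It is below one half only when the control rate is under about one third. These sizes rest on assumed rates, a yes/no definition of VAP, and unadjusted pairwise tests with complete data. The absence of any planned estimate or interval depends on none of these assumptions. That absence is the main reason to change the plan, because it leaves a non-significant VAP result open to misreading.

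**What to change.** In the Study population section, name the continuous outcome, the test and the sidedness to which the power calculation refers. Give the power that then applies at 51 per group: 0.80 only if one-sided, 0.71 if two-sided. State that the calculation does not cover VAP.

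In the Statistical analysis section, label VAP as a secondary outcome. Report each pairwise risk difference with a 95% confidence interval (for example Newcombe's) beside the chi-square or Fisher test. State that a non-significant VAP result will be interpreted through its interval.

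The cost is a few sentences and a few lines of analysis, with no extra patients. The drawback for the sponsor is that the stated power no longer appears to cover the whole aim.

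### The 51 per group matches only a one-sided two-group t-test; the stated 80% power for d = 0.5 is not met by two-sided t-tests (about 71%) or by the three-group ANOVA (60% to 74%)

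*Combined protocol and SAP*

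**What the plan says.** The power paragraph in the Study population section covers three arms, "the number of patients to be distributed to Group 1, Group 2, and the control groups". It names its calculator in one sentence: "The power analysis was done using GPower 1.3.9.2 software". The inputs are α = 0.05, d = 0.5 and 1−β = 0.80, and the outcome is given as "and the number of patients in each group was 51 for the power at" that value. To allow for missing data and deaths, "the number of patients was designed to be 56 for each group". The paragraph does not state the test family, one- or two-sided testing, the endpoint, or which arms the d of 0.5 separates.

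The Statistical analysis section sets out the tests. For normally distributed data it says: "Independent two-sample t-test, one-way analysis of variance will be used for the relationships between the variables that fit the normal distribution". Otherwise a rank test takes over, since "the Mann Whitney U test will be used for the variables that do not fit the normal distribution". Chi-square and Fisher tests are kept for categorical data. The significance rule is "All p values lower than 0.05 will be taken as significant in all results". No one-sided test is declared and no direction is given for any comparison.

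**The concern.** For a standardised difference of 0.5 at α = 0.05 and 80% power, the usual two-sided two-sample t-test needs 64 per group, so 51 is noticeably low. It is the one-sided answer. Nothing in the Statistical analysis section supports one-sided testing, and an ANOVA across three arms cannot be one-sided.

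This paragraph is the trial's only sample-size justification. A reader who accepts it will take the chance of missing a d of 0.5 to be 20%. If the planned tests carry a larger type II error, a non-significant comparison of the three cuff-control methods would look like stronger evidence of no difference than it is.

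**Working it through.** **Inputs.** From Study population: α = 0.05, d = 0.5, power 0.80, 51 per group (56 with the loss allowance), three equal groups. From Statistical analysis: two-sample t-test, one-way ANOVA and Mann-Whitney, all judged at p < 0.05. Assumption: an unqualified p < 0.05 means a two-sided t-test.

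**1. Reproducing 51.** For a two-sample t-test with n per group, the noncentrality is δ = d·√(n/2) on 2n − 2 degrees of freedom. One-sided power is P(T > t₀.₉₅), where T is noncentral t.

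- n = 50: δ = 0.5·√25 = 2.500, critical value 1.661, power 0.799
- n = 51: δ = 0.5·√25.5 = 2.525, critical value 1.660, power 0.806

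The smallest n reaching 0.80 is 51, which is the plan's figure exactly.

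**2. The same test, two-sided.** The critical value is now t₀.₉₇₅ and both tails count.

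| n per group | δ | critical value | power |
|---|---|---|---|
| 51 | 2.525 | 1.984 | 0.706 |
| 56 | 2.646 | 1.982 | 0.746 |
| 63 | 2.806 | 1.979 | 0.795 |
| 64 | 2.828 | 1.979 | 0.801 |

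The requirement is 64 per group. Solving for the d that gives power 0.80 yields 0.560 at n = 51 and 0.534 at n = 56.

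**3. Three-group ANOVA.** Power is P(F > F₀.₉₅) with 2 and 3n − 3 degrees of freedom and noncentrality λ = f²·3n, where f is the SD of the group means divided by the within-group SD. When the largest difference between arms is 0.5, f lies between two extremes:

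- third arm midway, means −0.25, 0, 0.25: f = √[(0.0625 + 0 + 0.0625)/3] = 0.204
- one arm differs, means 0, 0, 0.5: grand mean 0.1667, f = √[(2 × 0.0278 + 0.1111)/3] = 0.236

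| f | λ at 51 | power at 51 | λ at 56 | power at 56 | n for 80% |
|---|---|---|---|---|---|
| 0.204 | 6.375 | 0.603 | 7.000 | 0.647 | 79 |
| 0.236 | 8.500 | 0.736 | 9.333 | 0.779 | 59 |
| 0.25 (d/2) | 9.563 | 0.788 | 10.500 | 0.828 | 53 |

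The last row applies the two-group conversion f = d/2. It does not return 51 either: power is 0.797 at 52 and 0.805 at 53.

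**4. Mann-Whitney.** Multiplying n by the asymptotic relative efficiency for normal data, 3/π = 0.955, gives two-sided power of about 0.685 at 51 and 0.726 at 56. The requirement is 67 per group. The one-sided requirement is 53, so this does not reproduce 51.

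**5. The margin for losses.** Going from 51 to 56 implies a loss of 1 − 51/56 = 8.9%. With no loss at all, the two-sided t-test (0.746) and the ANOVA with a largest difference of 0.5 (0.647 to 0.779) still fall short of 0.80.

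**The case against.** The strongest reply is that two-sidedness is inferred. Neither section uses the term, and 51 is a correct answer for one standard test, so no sum is wrong in itself. That stands for the t-test and Mann-Whitney, where the shortfall rests on the conventional reading of p < 0.05. It does not help the ANOVA. If one-sided testing was intended, the analysis section would have to say so and give a direction for each comparison, and it does neither.

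A second reply is that d = 0.5 could have been entered as f = 0.25. The ANOVA then has 0.788 power at 51 and 0.828 at 56, close to or above target. This is a fair near miss. However, exact software would have returned 53, the plan states d and not f, and with three arms f = 0.25 corresponds to a largest difference of 0.25/0.4714 = 0.53 to 0.25/0.4082 = 0.61, not 0.5. The 56 is also reached only if nobody is lost.

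Third, the ANOVA range depends on patterns of means that the plan does not specify. That is true, and any restated figure should say so. The two patterns are the extremes, though, so no arrangement with a largest difference of 0.5 reaches 80% even at 56.

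Finally, no endpoint or source is given for d = 0.5, so the clinical importance of detecting 0.53 to 0.56 instead cannot be judged from the documents. That limits what can be said about consequences, but does not make the stated power correct.

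**Conclusion.** The concern holds. At the stated d, no reading of the planned tests that the documents support gives both 51 per group and 80% power.

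If t-tests are two-sided, the type II error at d = 0.5 with 51 evaluable per group is 1 − 0.706 = 29%, not 20%. For the ANOVA it is 26% to 40%, depending on where the third arm lies; this part needs no assumption about sidedness, only that 0.5 is the largest difference between arms. These figures are for a single test at 0.05. Bonferroni adjustment for three pairwise comparisons would lower t-test power at 51 to 0.538.

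The arithmetic is certain. The two-sided reading of the t-test is conventional but inferred.

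**What to change.** Keep 56 per group and rewrite the power paragraph. It should:

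- name the test, its sidedness, and the comparison and endpoint to which d = 0.5 applies;
- state that with 51 evaluable per group a two-sided 5% pairwise t-test has about 71% power for d = 0.5 (75% if all 56 are evaluable), or equivalently 80% power for d = 0.56 (0.53 at 56);
- give the three-group ANOVA power alongside: 0.60 (third arm midway) to 0.74 (one arm differs) at 51, for a largest difference of 0.5, saying that it depends on the pattern of means.

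The Statistical analysis section should state the same sidedness. The cost is rewording and a less favourable power figure; no patients are added and no test changes. Restoring 80% for the two-sided t-test would instead take 64 evaluable per group, or 64/(51/56) = 70.3, so 71 enrolled per group at the plan's implied loss.

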#### Intervention and Assessment

The appropriateness of patients who have received mechanical ventilator support using an ETT in the ICUs will be evaluated based on the inclusion and exclusion criteria. The patients who have been included in the study will be evaluated in terms of age, gender, height, weight, body mass index, medical diagnosis, chronic diseases, consciousness, presence of nasogastric (NG) tube, position, the reason for intubation, type of nutrition, drugs used (antibiotics, stress ulcer prophylaxis and sedative agents), Ramsay Sedation Score (RSS), transport and transfusion status, ventilator, respiration and hemodynamic values.

The cuff pressure of the patients in all groups will be controlled every eight hours. Smart cuff manager will be attached to the patients in study group 2. Samples will be taken from the

patients through open aspiration. The first deep tracheal secretion sample to be used to determine pepsin I level will be taken four hours after intubation. A sampling of the tracheal secretion samples to be used in the determination of pepsin II level will be initiated from the 5th hour after intubation and collected by the 24th hour of the intubation. A sampling of the tracheal secretion samples to be used in determination of pepsin III levels will be initiated from the 25th hour after intubation and collected by the 48th hour of the intubation or the patient is discharged or exitus.

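### Sedation, nasogastric tube and nutrition are recorded on every patient, but no planned test can use them in the pepsin comparison: a cheap precision gain of unknown size, not an error

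*Combined protocol and SAP*

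**What the plan says.** The Intervention and Assessment section lists what is assessed on included patients. The list contains "presence of nasogastric (NG) tube, position, the reason for intubation, type of nutrition" and, directly after, "drugs used (antibiotics, stress ulcer prophylaxis and sedative agents), Ramsay Sedation Score (RSS". It does not say when these items are recorded relative to randomisation or to the start of the allocated cuff method.

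The Statistical analysis section says of such attributes: "Patients' socio-demographic and clinical attributes, frequencies, percentage distribution, mean, and standard deviation will be provided". The tests it names are the two-sample t-test, one-way ANOVA, Mann-Whitney U, Pearson chi-square and Fisher's exact test. No regression, ANCOVA or other adjusted model appears, and pepsin is not mentioned there by name. Gender is the only factor on which the groups are to be balanced.

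The Study population section excludes patients "having contraindication of semi-sitting position, having a contraindication to enteral nutrition", and also those with reflux disease. The sample size is for "the number of patients to be distributed to Group 1, Group 2, and the control groups": alpha 0.05, d = 0.5 and power 0.80, from which "the number of patients in each group was 51". With an allowance for losses, "the number of patients was designed to be 56 for each group".

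**The concern.** The exclusions suggest that the plan regards position, feeding and reflux as relevant to aspiration of gastric content. Feeding, tube and sedation status are then collected on everyone, but none of the named tests can take a covariate. Any pepsin variance that these factors explain therefore stays in the error term. With about 51 patients per group and balance sought only on gender, a chance difference between groups in one of these factors also stays in the estimated effect.

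Precision is at stake. If the factors predict pepsin, an adjusted analysis would detect the same effect with fewer patients, or give more power at the planned size. Without a list fixed in advance, any adjustment made after an imbalance is noticed would be open to the charge of selection.

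**Working it through.** **Inputs from the documents (Study population):** alpha 0.05, d = 0.5, power 0.80, 51 per group before losses, three equal groups. The section states neither the test nor its sidedness. On method it says only "The power analysis was done using GPower 1.3.9.2 software".

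**Assumption:** R², the share of pepsin variance explained by the covariates. The documents give no figure, so a range from 0 to 0.30 is shown.

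**Step 1. Reproduce the 51.** For a two-sample t-test the noncentrality is d × √(n/2) = 0.5 × √(51/2) = 2.525, on 2 × 51 − 2 = 100 degrees of freedom.

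- One-sided: power 0.806, and 51 is the smallest n that reaches 0.80. This matches exactly.
- Two-sided: power 0.706 at 51; 64 per group would be needed.
- Three-group ANOVA with f = 0.25: noncentrality 3 × 51 × 0.25² = 9.56, power 0.788; 53 per group would be needed. This is close but not exact.

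The 51 therefore fits a one-sided t-test, or nearly a three-group ANOVA, but not a two-sided t-test. The starting power depends on which reading applies.

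**Step 2. Add covariates.** Adjustment divides the residual variance by 1/(1 − R²), so d becomes 0.5/√(1 − R²). For the ANOVA, the noncentrality is divided by (1 − R²). Three degrees of freedom are charged, leaving 97 for a pairwise comparison. Example at R² = 0.20: 2.525/√0.80 = 2.823, giving two-sided power 0.798.

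| Assumed R² | Two-sided pairwise power | One-sided pairwise power | Three-group ANCOVA, f = 0.25 | n per group for 80%, two-sided |
|---|---|---|---|---|
| 0 | 0.705 | 0.806 | 0.788 | 64 |
| 0.02 | 0.714 | 0.813 | 0.797 | 63 |
| 0.05 | 0.727 | 0.823 | 0.810 | 61 |
| 0.10 | 0.750 | 0.841 | 0.832 | 58 |
| 0.20 | 0.798 | 0.877 | 0.875 | 52 |
| 0.30 | 0.848 | 0.912 | 0.916 | 45 |

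If the covariates explain nothing, two-sided power falls from 0.706 to 0.705. Gender in the model would take one further degree of freedom, which is not charged above. Since three cost 0.001 of power, one more is negligible. If all 56 per group were evaluable, the two-sided figures at R² of 0, 0.10, 0.20 and 0.30 would be 0.746, 0.789, 0.834 and 0.880.

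**Step 3. What R² might a yes/no covariate reach?** If a share p of patients has the factor and it shifts pepsin by b residual SDs, then R² = b²p(1 − p)/(1 + b²p(1 − p)). Both cases below are illustrative.

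- p = 0.9, b = 0.5: 0.0225/1.0225 = 0.022.
- p = 0.5, b = 1: 0.25/1.25 = 0.20.

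A factor that nearly every patient shares buys about one point of two-sided power (0.706 to 0.714). A strong and evenly split factor buys about nine (0.706 to 0.798).

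**Step 4. Chance imbalance.** The SD of the difference in a standardised covariate between two groups of 51 is √(2/51) = 0.198. A difference of 0.3 SD or more is 0.3/0.198 = 1.515 standard errors, which has a probability of about 13% for one covariate and one pair of groups.

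**The case against.** The strongest reply is that nothing is broken. The trial is randomised, so the unadjusted tests are valid, and chance imbalance in feeding or sedation is already covered by their standard error and significance level. This stands. A reader might infer from the imbalance figures that the unadjusted result is biased. For example, an imbalance at its 95% edge (1.96 × 0.198 = 0.39 SD) in a factor correlated 0.45 with pepsin shifts the difference by 0.39 × 0.45 = 0.18 SD, about a third of d = 0.5. But 0.45² is about 0.20, so this is the R² = 0.20 row of the table seen from another side. The shift is equally likely in either direction and is not a further harm.

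Other parts of the reply also stand:

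- **The gain is not demonstrated.** No R² is given, and excluding patients who cannot be enterally fed may leave nutrition type, and perhaps tube status, almost uniform. That exclusion does not settle how included patients are fed, however, and no exclusion restricts sedation.
- **Adjustment cannot be said to repair an underpowered trial.** The rise from 0.71 to 0.80 needs two-sided testing and an R² of about 0.20, and the documents state neither. On the one-sided reading that gives 51 exactly, power is already 0.806. The unstated sidedness moves power by 0.806 − 0.706 = 0.10, about as much as adjustment at R² = 0.20.
- **The plan does not itself mark sedation as relevant.** The exclusions concern position, feeding and reflux; the case for the Ramsay score rests on clinical plausibility.
- **The change is not free.** No recording time is given, and patients may have been ventilated for up to 48 hours at first assessment. The list also includes items that can accrue later, such as transport and transfusion. Adjusting for sedation or feeding recorded after allocation could introduce bias.
- **The section is not purely descriptive.** It also speaks of testing relationships between variables, so attributes might be compared between groups. That would still not adjust the pepsin comparison.

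**Conclusion.** The point holds as a recommended improvement, not as a correction. Useful covariates are collected and no planned analysis of pepsin can use them. A short pre-specified adjustment would cost about 0.001 of power if they explain nothing. At 51 per group, d = 0.5 and two-sided pairwise testing, it would add about 4 points at an assumed R² of 0.10, 9 at 0.20 and 14 at 0.30, but only 1 to 2 points at 0.02 to 0.05. On a one-sided reading, power rises from 0.806 to 0.912 over an R² of 0 to 0.30.

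These figures rest on an assumed R², on the d in the plan, on approximately normal errors after transformation, and on covariates measured before the allocated method begins. A reader might go further and call the planned analysis invalid, or the trial short of power for want of adjustment. The documents support neither.

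**What to change.** In the Statistical analysis section, pre-specify a linear model for each of the later pepsin measures (II and III):

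- **Scale:** log pepsin with a fixed rule for undetectable values, or ranks. The plan already foresees non-normal data, so this choice must be made in advance.
- **Terms:** group; gender, because the groups are balanced on it; and a short list comprising Ramsay score, type of nutrition, and tube status if it varies.
- **Timing of the choice:** fix the list before any pepsin result is seen.
- **Supporting analysis:** keep the unadjusted comparison.

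In the Intervention and Assessment section, state that the covariate values are recorded before the allocated cuff method starts, and exclude from the model any value recorded later. Pepsin I is not on the list because the text does not say that the four-hour sample precedes the allocated method.

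The cost is wording, a few degrees of freedom and the discipline of a fixed recording time. No new variable is needed, though a pre-allocation value of each must be confirmed to exist.

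### Pepsin I, sampled at hour 4, has no stated role: the plan neither separates it from the later samples nor uses it to adjust them

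*Combined protocol and SAP*

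**What the plan says.** The Aim section asks about the effect of the cuff-control methods "on preventing microaspiration of gastric content and on VAP development within 48 hours after intubation".

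The Intervention and Assessment section defines three pepsin samples:

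- Pepsin I: "The first deep tracheal secretion sample to be used to determine pepsin I level will be taken four hours after intubation".
- Pepsin II: "pepsin II level will be initiated from the 5th hour after intubation and collected by the 24th hour of the intubation".
- Pepsin III: "pepsin III levels will be initiated from the 25th hour after intubation and collected by the 48th hour of the intubation", with an earlier end at discharge or death.

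None of the three is called baseline, primary or secondary.

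On the intervention, the same section says "The cuff pressure of the patients in all groups will be controlled every eight hours" and "Smart cuff manager will be attached to the patients in study group 2". It gives no start for the eight-hour clock and no time for allocation or for attaching the device.

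On entry, the Study population section excludes "patients who have spent more than 48 hours on a mechanical ventilator at the initial assessment", so a patient may already have spent a good part of two days on the ventilator when assessed.

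The Statistical analysis section does not mention pepsin. For continuous data it says "Independent two-sample t-test, one-way analysis of variance will be used for the relationships between the variables that fit the normal distribution", with Mann-Whitney U for non-normal variables. It contains no covariate adjustment, change score or repeated-measures model, and any p value under 0.05 counts as significant.

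**The concern.** The three samples do not carry the same information about cuff control. Pepsin II and III are collected over long windows, most or all of which can fall under the allocated method. Pepsin I comes early, and part of what it measures may come from aspiration that no cuff method could have influenced.

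Two consequences follow if the plan is applied as written. First, nothing stops a between-arm difference in pepsin I from being counted like a difference in pepsin II or III, although it bears least on the question asked. Second, a sample that every patient is due to give, and that may predict the later values, is never used to reduce between-patient variation in pepsin II and III. The first affects how results are interpreted. The second costs precision in a trial of modest size.

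**Working it through.** **1. How much exposure can pepsin I carry?** If the method starts no earlier than intubation, the upper limit at hour 4 is 4 hours, which is 4/8 = half of one check interval. How much of that follows a scheduled check depends on a clock the protocol does not define:

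- First check at intubation: up to 4 of 4 hours.
- First check 8 hours after intubation: 0 of 4 hours.
- Checks at fixed clock times, with the time U to the first check assumed uniform on 0 to 8 hours: P(U > 4) = 4/8 = 0.5, and the mean time after a check is ∫₀⁴ (4 − u)/8 du = 1 hour.

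The range is therefore the whole of 0 to 4 hours. These figures count scheduled checks. They do not measure exposure to the continuous device, whose start time is also unstated. For late entrants, hour 4 may have passed before enrolment.

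**2. The plan's own sample size.** Inputs from Study population: d = 0.5, α = 0.05, power 0.80, 51 per group. That section ties d to no particular pepsin sample and does not state sidedness.

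- Two-sample t-test, one-sided: n = 50.15, rounded up to 51. The stated figure is reproduced, with power 0.806 at 51.
- Two-sided: n = 63.77, rounded up to 64, with power 0.706 at 51.

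Both versions are carried forward, so that the question of sidedness does not drive the result.

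**3. What adjustment for pepsin I could gain.** Let ρ be the within-arm correlation between pepsin I and a later sample. Analysis of covariance multiplies residual variance by 1 − ρ², so the effective standardised difference is 0.5/√(1 − ρ²). The documents do not give ρ; the values below are assumptions. Power is for one pairwise comparison with 51 per group, ignoring the single degree of freedom spent on the covariate.

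| ρ (assumed) | 1 − ρ² | Variance removed | Effective d | Power, two-sided | Power, one-sided |
|---|---|---|---|---|---|
| 0 (unadjusted) | 1.00 | 0% | 0.500 | 0.71 | 0.81 |
| 0.2 | 0.96 | 4% | 0.510 | 0.72 | 0.82 |
| 0.3 | 0.91 | 9% | 0.524 | 0.75 | 0.84 |
| 0.5 | 0.75 | 25% | 0.577 | 0.82 | 0.89 |
| 0.7 | 0.51 | 49% | 0.700 | 0.94 | 0.97 |

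At ρ = 0.5 the two-sided comparison passes the 0.80 target without a further patient or sample. At ρ = 0.2 the gain is about 0.02.

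**4. Is pepsin I a legitimate covariate?** If it is taken before the allocated method starts, yes. If the method starts first, pepsin I is a post-treatment value, and adjusting for it can remove part of a real early effect. The documents do not settle which case applies.

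**The case against.** Randomization already protects the unadjusted comparison: its type I error rate covers chance imbalance in early pepsin. Adjustment therefore improves efficiency and does not correct a bias. This stands. The gain also rests on an assumed correlation. If pepsin I records a one-off event around intubation, ρ could be low and the benefit slight. On the one-sided reading that reproduces 51, power is already 0.81. Both points stand and limit the size of the claim.

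The plan also never calls pepsin I an outcome. That status is inferred from the parallel naming and from an analysis section that makes no distinction. The inference is fair, but the fault is an unstated role rather than a declared wrong one.

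A reader might be tempted to go further, in four ways that the documents do not support:

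- *Pepsin I precedes the first cuff check.* True only if the clock starts at intubation and the first check falls at hour 8. A check at intubation would come before the sample.
- *Pepsin I mostly reflects aspiration at intubation.* Plausible, but no text or figure gives a proportion.
- *Pepsin from intubation carries over into pepsin II.* The documents say nothing about how long pepsin persists.
- *Any arm difference in pepsin I must be chance or related to intubation.* The device may be attached before hour 4, and if the allocated method governs the initial cuff inflation, that is part of the treatment. A difference could be a true early effect.

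What survives is that the plan states neither the timing nor the role of pepsin I, and that it makes no analytic use of it.

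**Conclusion.** The point holds as a cheap improvement to the plan, not as a flaw that invalidates it. Whichever way the missing timing is resolved, the plan needs a different treatment of pepsin I: if it precedes the allocated method it is an unused baseline, and if it follows, it is a brief-exposure value that should not carry the conclusion about cuff control.

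The possible gain in two-sided power runs from about 0.02 to 0.23 for ρ from 0.2 to 0.7 (0.938 − 0.706 = 0.232 at the top). One-sided, it runs from about 0.01 to 0.16 (0.969 − 0.806 = 0.163). This assumes d = 0.5 applies to the later sample, 51 evaluable patients per group, a roughly linear relation on the analysis scale, and a covariate unaffected by treatment. It is a gain in precision; no bias in the unadjusted comparison is claimed.

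**What to change.** 1. State in the protocol when allocation, the first cuff check and device attachment occur, and record for each patient when the allocated method started relative to the hour-4 sample. Say what is done for patients enrolled after hour 4, whose sample may be missing.
2. State that conclusions about cuff method rest on pepsin II and III, not on pepsin I.
3. Compare pepsin II and III across the three arms by analysis of covariance with pepsin I as covariate, on a log or rank scale if the values are skewed.
4. If pepsin I precedes the allocated method, make the adjusted analysis the main one. Otherwise keep the unadjusted analysis as main, show the adjusted one as supportive, and report pepsin I separately as an early value. Fix this choice before pepsin results are seen by arm.

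The cost is a few lines of text and one recorded time per patient; no extra sample or patient is needed. The downside is that, if the method starts before hour 4, adjustment may absorb some early effect, which is why both results are shown. Moving allocation to after hour 4 would make pepsin I a clean baseline. It would also take the first four hours out of the comparison and leave cuff control in that period undefined, so it is a design question for the sponsor and not part of this recommendation.
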